#### 10.1.1.3 Calculation of AUC

- The minimum requirement for the calculation of AUC will be the inclusion of at least 3 consecutive plasma concentrations above the lower limit of quantification (LLOQ), with at least one of these concentrations following  $C_{max}$ .
- All AUC values will be calculated using the 'linear up / log down' trapezoidal rule where the linear trapezoidal rule will be used for increasing concentrations and the log trapezoidal rule for decreasing concentrations.

### 10.2 Urine PK Analysis (SAD-HS only)

All PK summary tables will be based on the Urine PK Population for concentration data. All analyses will be summarized as described in section 3.1 (PK - continuous descriptive analysis). All listings will be based on the Enrolled Population. All missing and BLQ handling of urine concentrations for PK analysis will be based on section 3.5.

For SAD-HS, the urinary output will be collected during the intervals -6-0 predose, and 0-6, 6-12, 12-18 hours post dose on Day 1, 18-24, 24-30, 30-36 hours post dose on Day 2, 36-42, 42-48 hours post dose on Day 3.

The following urine pharmacokinetic parameters of EP547 (and its metabolites if applicable) will, where possible, be determined from the urine collection volume and concentrations of the analyte(s) by non-compartmental method using Phoenix WinNonlin software (Version 8.1 or higher):

Parameter	Definition
$Ae_{t1-t2}$	Total amount of the analyte excreted in urine from time t1 to t2 hours (for each urine time interval) $Ae_{t1-t2} = Cu_{t1-t2} \times Vu_{t1-t2}$ , where Vu = the volume of urine collected and Cu = the concentration of urine in each collection interval sample
CAe	Cumulative amount excreted in urine considering time 0 to 48 hours. $CAe = Cu_{0-48} \times Vu_{0-48}$
$Fe_{t1-t2}$	Fraction of the administered dose the analyte excreted into the urine from time t1 to t2 hours (for each urine time interval) $Fe_{t1-t2} = \left( \frac{Ae_{t1-t2}(mg)}{Dose(mg)} \right) \times 100$
CFe	Cumulative fraction of the administered dose the analyte excreted into the urine considering time 0 to 48 hours. $Fe_{0-48} = \left( \frac{Ae_{0-48}(mg)}{Dose(mg)} \right) \times 100$
CLr	Renal clearance calculated as $CLr = \text{Cumulative Ae} / \text{Plasma AUC}_{0-48}$
Corrected Urine Fe for metabolite	(Fe metabolite in urine) * (Molecular Weight of parent drug/ Molecular Weight of metabolite)
Corrected Urine Ae for metabolite	(Ae metabolite in urine) *(Molecular Weight of parent drug/ Molecular Weight of metabolite)

The additional parameters for urine Corrected Fe & Corrected Ae for metabolite will be derived for SAD-HS for each urine sample interval.(ie; Fe (0-6hr), Fe(6-12 hr), Fe(12-18 hr) etc..).

PK concentration and parameter data will be analyzed descriptively as noted in section 3.1.

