### 3.5 Handling of Missing Data

For the classification of Treatment emergent adverse event (TEAE) and Concomitant medication, the following will be applied in the following order:

- a. If all dates/times (start and stop) missing, the event/medication will automatically be classified as a TEAE/Concomitant medication.
- b. For adverse events (AEs) with a missing start date/time, if the event end date/time is prior to first study drug administration, the event will not be classified as a TEAE.
- c. If only the AE start year/ medication end year is present and is the same or is after the first study drug administration year unit, the event/medication will be classified as a TEAE/Concomitant medication.
- d. If the AE start month and year/medication end month and year are present and are the same or after the first study drug administration month and year units, the event/medication will be classified as a TEAE/Concomitant medication.

For the PK analysis the following will be applied:

- a. For the concentration descriptive summaries, concentrations may be excluded if sampling time deviation is considered large to affect the profile at the discretion of the pharmacokineticist.
- b. Concentrations (plasma and skin) that are below limit of quantification (BLQ which is 10 ng/mL undiluted) prior to the first quantifiable value will be set equal to zero. Post dose BLQ concentrations will be set to missing.
- c. Where there are no results (NR), these will be set to missing.
- d. If more than 75% of values per nominal timepoint and treatment group are BLQ, then all descriptive statistics, except for nBLQ, will be denoted as not calculable (NC).
- e. For the calculation and graphical representation (semi-log and log-log plots) of geometric descriptive statistics, 0 values will be set to missing.
- f. For the purpose of calculating the non-compartmental PK parameters, plasma concentrations that are BLQ prior to the first quantifiable value will be set equal to zero. BLQ values after measurable concentrations will be set to missing.
- g. For the calculation of summary statistics of PK parameters, all NR and NC values in a data series will be set to missing.

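### SAP 10.2 codes a collected urine interval with BLQ drug as missing, like an uncollected one: interval Ae and Fe are biased upward, and the cumulative parameters are either lost or exposed to uncollected intervals counted as zero

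*SAP*

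**What the plan says.** SAP 10.2 has no BLQ or missing-data rule of its own for urine: "All missing and BLQ handling of urine concentrations for PK analysis will be based on section 3.5". The relevant items in section 3.5 are these.

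- Item (b) is worded for plasma and skin, "Concentrations (plasma and skin) that are below limit of quantification (BLQ which is 10 ng/mL undiluted", and adds: "Post dose BLQ concentrations will be set to missing".
- Item (c): "Where there are no results (NR), these will be set to missing".
- Item (f), for non-compartmental parameters, is worded for plasma. There, "plasma concentrations that are BLQ prior to the first quantifiable value will be set equal to zero", and "BLQ values after measurable concentrations will be set to missing".

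SAP 10.2 defines interval Ae as "Total amount of the analyte excreted in urine from time t1 to t2 hours (for each urine time interval", computed as concentration × volume. CAe is "Cumulative amount excreted in urine considering time 0 to 48 hours", written as Cu(0-48) × Vu(0-48). CFe is the 0-48 h amount as a percentage of dose. CLr is cumulative Ae divided by plasma AUC0-48. Neither document says how a missing interval enters CAe, and no rule uses the recorded volume to tell a BLQ sample from one that was never collected.

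**The concern.** In plasma, leaving off trailing BLQ points is reasonable because AUC0-t stops at the last measurable value. Urine parameters are amounts. A collected interval with BLQ drug has a nearly known amount close to zero; an uncollected interval has an unknown amount. Once the section 3.5 rules are imported, both carry the same code, although they need different treatment.

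Ae, Fe and CLr are named secondary PK outcomes (Protocol 15.2.2, SAP 2.3.2). Urine is collected only in SAD-HS, with six active subjects per dose level (Protocol 7.1.1), so one lost or distorted value shows in the summary.

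**Working it through.** The plan gives no figure to reproduce. The check traces the rule through the parameters and then illustrates the size.

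**Inputs from the documents.** Eight 6-hour post-dose intervals to 48 h (Protocol 12.2). Single doses of 25 to 675 mg (Protocol Addendum, section 5). A half-life of about 18 h, observed in monkeys (Protocol 5.3). A limit of 10 ng/mL, stated for plasma and skin only (SAP 3.5).

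**Assumptions.** The 10 ng/mL limit also applies to urine; 250-1000 mL of urine per interval; mono-exponential excretion parallel to plasma.

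**1. What each reading does.**

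| | Collected, BLQ | Not collected |
|---|---|---|
| Interval Ae, Fe | Missing; should be about 0 | Missing; correct |
| CAe, CFe, CLr if missing propagates | Not calculable, needlessly | Not calculable; correct |
| CAe, CFe, CLr if missing is skipped | Counts as 0; acceptable | Counts as 0; wrong |

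Neither cumulative reading handles both columns well.

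**2. Interval summaries.** Suppose k of 6 subjects are BLQ in an interval and the other 6 − k have mean amount m. The planned summary reports m. With the BLQ amounts at 0 the mean is m(6 − k)/6. For k = 3 that is m/2, so the reported mean is up to 2 times the mean over all six. If volumes are similar, every BLQ amount lies below every quantifiable amount, so the bias can only be upward.

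**3. What a BLQ interval can hide.** The maximum is LLOQ × volume: 10 ng/mL × 250 to 1000 mL = 2.5 to 10 µg, or 0.01% to 0.04% of 25 mg. Under propagation this small uncertainty removes the subject's CAe, CFe and CLr.

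**4. What an uncollected interval costs if skipped.** The share of the 0-48 h amount in the interval starting at a is (2^(−a/18) − 2^(−(a+6)/18)) / (1 − 2^(−48/18)). For 0-6, 6-12 and 12-18 h this gives 24.5%, 19.4% and 15.4%; for 42-48 h it gives 4.9%. CFe and CLr are proportional to CAe, so all three fall by the same percentage. With an assumed 4 h half-life the 0-6 h share is about 65%.

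**5. A very low excretor.** Take 0.2% of 25 mg excreted (50 µg), an 18 h half-life and 500 mL per interval. Concentrations are 24.5, 19.4, 15.4, 12.2, 9.7, 7.7, 6.1 and 4.9 ng/mL, so the last four are BLQ. The four quantifiable intervals sum to 35.8 µg.

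- Last four at zero: 35.8/50 = 0.72.
- At LLOQ/2: add 4 × 5 ng/mL × 500 mL = 10 µg; 45.8/50 = 0.92.
- At LLOQ: add 20 µg; 55.8/50 = 1.12.
- SAP formula read as mean non-missing Cu × total volume: 17.9 ng/mL × 4000 mL = 71.6 µg; 71.6/50 = 1.43.
- Missing propagates: not calculable.

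Zeroing omits 14.2 µg: 28% of CAe, though only 0.057% of the dose.

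**The case against.** Several counter-arguments have force.

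- **A reader might infer that Ae, CAe, CFe and CLr are all wrong in one case or the other.** The documents do not support that. Interval Ae for an uncollected interval is correctly missing. Under propagation the cumulative values are lost, not wrong. Under skipping, a BLQ interval contributes zero, which is what the fix does.
- **A reader might take 15-25% as the harm from the BLQ rule.** It is not. It comes only from uncollected intervals that are skipped, and it rests on a monkey half-life.
- **Missed collections may be rare and can be reviewed.** Urine is collected during mandatory confinement through 48 h (Protocol 7.1.4.1). The Urine PK population is decided subject by subject and excludes important deviations (SAP 4.1.3). This lowers the likely frequency but does not say how CAe is computed for a subject who stays in. The same population also requires a measurable urine concentration, which selects in the upward direction.
- **BLQ and no-result samples stay distinguishable.** SAP 3.1 counts BLQ values separately for plasma and skin concentration summaries, and a urine concentration listing is planned. That helps a reader of the listing; it does not change the parameter calculation.
- **Late BLQ urine implies negligible excretion.** With an 18 h half-life and 500 mL, the 42-48 h interval is BLQ only if CAe is below 5 µg/0.0486 = 103 µg, or 0.41% of 25 mg. This is fair, but it depends on the half-life: at an assumed 4 h, a subject excreting 20% of 25 mg still has 4.5 ng/mL in the last interval.
- **Section 3.5 never names urine.** Read that narrowly, urine has no BLQ rule at all, which is also a gap.

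**Conclusion.** The point holds in limited form. The stated rule is wrong for urine amounts: it drops a collected interval whose amount is bounded near zero, and so biases interval Ae and Fe summaries upward. For CAe, CFe and CLr the outcome depends on a choice the SAP does not make. Propagation needlessly loses values for low excretors; skipping counts uncollected intervals as zero against the full AUC0-48, by about 15-25% for one of the first three intervals under the illustrative 18 h half-life. The actual size is unknown, because urine LLOQ, volumes, excretion and missed-collection rates are not given.

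A reader might also infer that dose selection in uremic subjects is at risk. The documents do not support this: MAD-UP dosing rests on SD-UP data and predicted steady-state concentrations (Protocol 7.1.3), and the urine parameters are descriptive.

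**What to change.** In SAP 10.2, replace the cross-reference to section 3.5 for urine parameters with a urine rule:

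1. A collected interval with a recorded volume and a BLQ concentration has Ae = 0. Repeat with LLOQ/2 or LLOQ × volume as a sensitivity check, because zeroing can understate CAe when excretion is very low.
2. An uncollected interval, or one with no result, stays missing.
3. CAe is the sum of the interval Ae values over 0-48 h.
4. If any 0-48 h interval is uncollected, report the available interval Ae and set CAe, CFe and CLr to NC.

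Computing CLr over the longest complete window from time zero is not a full substitute: there is no such window when 0-6 h is lost.

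The cost is a few sentences in the SAP and a small programming change, with no new data. The downside is slightly fewer CLr values where collections were missed, and a downward bias in very low excretors that is small relative to dose and that the sensitivity check makes visible.

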12.2. Urine Collection for Pharmacokinetics (SAD-HS Only)

Urine sampling for PK of EP547 will be collected at predose (-6 to 0 hours) and from >0 to 6, >6 to 12, and >12 to 18 hours postdose on Day 1; >18 to 24, >24 to 30, and >30 to 36 hours postdose on Day 2; and >36 to 42 and >42 to 48 hours postdose on Day 3.

12.3. Skin Biopsy for Pharmacokinetics (Last Dose Level for MAD-HS and All Dose Levels for MAD-CP and MAD-UP Only)

Given that EP547 is hypothesized to be an inverse agonist (inhibitor) of MRGPRX4 in the skin to reduce itch, three 3-mm biopsies of the skin from the back will be performed under local anesthesia on Day 1 at 2 hours postdose with an assessment window of +30 minutes. One biopsy will be used for PK to evaluate drug concentrations at the site of action and the other 2 biopsies will be used for PD assessment as described in Section 14.5 to further elucidate the mechanism of action of EP547.

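### SAP 10.2 leaves the 0–48 h urinary amount without a usable definition, and its BLQ rule biases the interval Ae and Fe summaries upward

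*SAP*

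**What the plan says.** Protocol 12.2 and SAP 10.2 agree on the collections in SAD-HS: one predose interval (-6 to 0 h) and eight consecutive 6-hour postdose intervals, which the SAP lists as "0-6, 6-12, 12-18 hours post dose on Day 1, 18-24, 24-30, 30-36 hours post dose on Day 2, 36-42, 42-48 hours".

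The parameter table in SAP 10.2 defines:

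- the interval amount, Ae(t1-t2), as Cu(t1-t2) × Vu(t1-t2), "where Vu = the volume of urine collected and Cu = the concentration of urine in each collection interval sample";
- CAe, described as "Cumulative amount excreted in urine considering time 0 to 48 hours", as Cu(0-48) × Vu(0-48), with no summation;
- CFe as Ae(0-48) divided by dose, times 100;
- CLr as cumulative Ae divided by plasma AUC(0-48).

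On values below the limit of quantification, SAP 10.2 says: "All missing and BLQ handling of urine concentrations for PK analysis will be based on section 3.5". Item b of section 3.5 names plasma and skin concentrations. It sets BLQ values before the first quantifiable one to zero, then adds: "Post dose BLQ concentrations will be set to missing". Item f gives the corresponding rule for plasma NCA: BLQ after measurable concentrations becomes missing. Item d suppresses descriptive statistics only when more than 75% of values at a timepoint and treatment group are BLQ. Section 3.5 has no urine-specific rule.

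**The concern.** There are two separate gaps.

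First, no 0–48 h pooled sample is planned, and Cu has a meaning only for a single interval sample. Cu(0-48) is therefore undefined. CFe and CLr take their numerator from CAe, so for any one subject an error in CAe carries over to both in proportion.

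Second, a BLQ urine sample with a recorded volume is informative: almost nothing was excreted in that interval. Treating it as missing removes the low excreters from that interval's Ae and Fe summaries and leaves the higher ones. This should occur mainly in late intervals and at low doses, where BLQ samples are most likely.

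Ae, Fe and CLr are listed secondary outcomes (Protocol 15.2.2, SAP 2.3.2), and SAD-HS is the only segment with urine PK.

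**Working it through.** The documents give no urine result, so there is no stated figure to reproduce.

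**Cumulative amount**

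The target is CAe = Σ Cu_i × Vu_i over the eight intervals. Two readings of Cu(0-48) were compared with it.

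- Volume-weighted: Cu(0-48) = Σ(Cu_i × Vu_i) / ΣVu_i. Multiplying by ΣVu_i returns the sum exactly, a ratio of 1.000 in every case.
- Unweighted: Cu(0-48) = mean of the eight Cu_i, multiplied by ΣVu_i. This equals the sum only in special cases, such as equal volumes.

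Worked example. The assumptions are one-compartment excretion, absorption rate 1/h, half-life 18 h (the monkey value in Protocol 5.3) and 1 mg recovered over 48 h. The volumes are invented.

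| Interval (h) | Amount (mg) | Volume (mL) | Concentration (ng/mL) |
|---|---|---|---|
| 0–6 | 0.2088 | 600 | 348.0 |
| 6–12 | 0.2035 | 500 | 407.1 |
| 12–18 | 0.1616 | 250 | 646.6 |
| 18–24 | 0.1283 | 200 | 641.5 |
| 24–30 | 0.1018 | 600 | 169.7 |
| 30–36 | 0.0808 | 500 | 161.6 |
| 36–42 | 0.0641 | 250 | 256.6 |
| 42–48 | 0.0509 | 200 | 254.6 |

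Total volume is 3,100 mL. The concentrations sum to 2,885.7, so their mean is 2,885.7 / 8 = 360.7 ng/mL. The unweighted product is 360.7 × 3,100 = about 1,118,000 ng = 1.118 mg against a true 1.000 mg, an overstatement of 12%.

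Ratio of the unweighted product to the true total, over further assumptions:

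| Volumes | Half-life | Ratio |
|---|---|---|
| Equal | 6–30 h | 1.00 |
| Three unequal patterns | 18 h | 1.04 to 1.33 |
| Three unequal patterns | 6–30 h | 0.82 to 1.65 |
| Random lognormal, median 400 mL, log-SD 0.4 | 18 h | median 1.13 (5–95%: 1.01 to 1.37) |
| Random lognormal, same | 6 h | median 1.11 (5–95%: 0.87 to 1.55) |

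The error is usually upward, but it can be zero or negative.

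**BLQ in one interval**

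Protocol 7.1.1 gives 6 EP547 subjects per dose level. Let b of them be BLQ and m be the mean amount in the other 6 - b. Setting BLQ to missing reports m. Counting BLQ as zero gives m × (6 - b)/6. The ratio is 6/(6 - b).

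| BLQ of 6 | Percent BLQ | Summary reported under item d? | Reported mean / mean with zeros |
|---|---|---|---|
| 1 | 17% | yes | 1.2 |
| 2 | 33% | yes | 1.5 |
| 3 | 50% | yes | 2.0 |
| 4 | 67% | yes | 3.0 |
| 5 | 83% | no | – |

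The table takes item d to reach the derived Ae and Fe summaries. Against the unknown true amounts these ratios are upper limits, because a BLQ sample holds something between zero and the limit times the volume.

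**BLQ in the 0–48 h total**

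SAP 3.5 gives a limit of 10 ng/mL; its use for urine is an assumption. At a generous 1,000 mL per interval, a BLQ interval holds at most 10 × 1,000 = 10,000 ng = 0.01 mg. That is 0.01/25 = 0.04% of the lowest dose, 25 mg. Eight such intervals hold at most 8 × 0.04% = 0.32%. At 400 mL per interval the bounds are 0.016% and 0.128%.

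**The case against.** On CAe, the case for the plan is good. The parameter is called cumulative, interval amounts are derived anyway, the CLr numerator is labelled cumulative Ae, and SAP 10.4.2 selects a urine NCA model. All of this points to the sum. A reader might infer from the printed formula that CAe, CFe and CLr will come out wrong, always too high, or several-fold too high through adding the concentrations. The documents support none of these. The volume-weighted reading is exact, no section prescribes an unweighted mean or a sum of concentrations, and the unweighted mean can err downward. What stands is that the weighting is unstated, and the volume-weighted concentration can be computed only from the sum that the SAP omits.

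On BLQ, items b and f of section 3.5 are written for plasma and skin, so it can be argued that they do not govern urine. But SAP 10.2 refers urine to that section without exception, and no other rule is offered. The effect on the 0–48 h total is indeed negligible. The effect on the interval summaries is not.

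On importance, a reader might infer that a misstated renal share would feed into dosing of the dialysis subjects. Protocol 7.1.3 caps the SD-UP dose by the third SAD-HS dose and bases the MAD-UP dose on SD-UP data. Plasma PK is measured directly in those subjects (Protocol 12.1), and no dosing rule uses Ae, Fe or CLr.

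**Conclusion.** The point holds in two limited parts.

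- CAe is ambiguously defined. This becomes a numerical error only if it is programmed with an unweighted concentration. The 0.82 to 1.65 range shows what that could do under assumed volumes and half-lives; it is not an estimate for this trial.
- The BLQ cross-reference is a stated rule that biases the interval Ae and Fe summaries upward, by up to a factor of 3 when 4 of 6 subjects are BLQ. How often this occurs cannot be judged from the documents.

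The two parts also interact. Once CAe is a sum, an interval set to missing for BLQ could make a subject's total not calculable over at most about 0.04% of a 25 mg dose, and the SAP does not say how a missing interval enters the total.

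The parameters are secondary and summarised descriptively. Severity is minor to moderate.

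**What to change.** In SAP 10.2:

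1. Define CAe(0-48) as the sum of Ae(t1-t2) over the eight postdose intervals. State that this quantity is Ae(0-48) in CFe and cumulative Ae in CLr.
2. Replace the reference to section 3.5 with a urine rule. If the volume is recorded and the concentration is BLQ, set Ae and Fe for that interval to 0. Treat them as missing only when the sample or the volume is missing.
3. When an interval is missing, report CAe, CFe and CLr as not calculable, or flag them as incomplete.

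The cost is a few lines of SAP text and the matching programming specification. The planned collections already supply everything needed.

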### 10.3 Skin PK Analysis

All PK summary tables will be based on the PK Population for skin concentration data. All skin concentrations will be summarized as described in section 3.1 (PK - continuous descriptive analysis). A listing will be provided for the same based on the Enrolled Population.

For last dose level for MAD-HS and all dose levels for MAD-CP and MAD-UP, Skin EP547 and metabolites (as applicable) concentrations will be summarized.

## 10.4 Pharmacokinetic Noncompartmental Analysis (NCA)

### 10.4.1 General Plasma NCA Pharmacokinetic Settings

The general settings in Phoenix WinNonlin® for generation of plasma PK parameters are as listed below.

- NCA Model Type Plasma (200-202)
- Weighting Uniform
- AUC Calculation Method: Linear Up/Log Down
- Dose Options Type Extravascular
- Slopes Setting Fit Method: Best Fit
- Rsq\_Adjusted Criteria for 'λz' 0.8
- AUC% extrapolation Criteria 20

### 10.4.2 General Urine NCA Pharmacokinetic Settings

The general settings in Phoenix WinNonlin® for generation of urine PK parameters are as listed below.

- NCA Model Type: Urine (210-212)
- Weighting: Uniform
- AUC Calculation Method (if applicable): Linear Up/Log Down

### 10.4.3 Inferential Analyses

For SAD-HS and MAD-HS, the following endpoints will be analyzed as described in section 3.3:

- Dose proportionality:
  - $C_{\text{trough}}$  (Only Day 7 value to be used to assess DP for MAD )
  - $C_{\text{max}}$
  - $AUC_{0-t}$
  - $AUC_{0-\text{inf}}$
  - $AUC_{0-\tau}$  (as appropriate, MAD only)

Dose proportionality will be assessed graphically ( $C_{\text{max}}$ ,  $AUC_{0-t}$  and  $AUC_{0-\text{inf}}$  versus dose) on log scale for both axes. PK parameters derived from Day 1 (SAD & MAD) and Day 7 (MAD) will be subjected to dose proportionality assessment for entire dose range studied for EP-547-101. From each model, the slope of the regression line  $\beta$  will be presented along with the 90% CI of the slope. The regression line formulae along with correlation coefficient ( $r^2$ ) will be presented in the plot.

Sample SAS Code for dose-proportionality analysis using power model. Programmers will need to modify as appropriate to the study:

```
proc mixed;  
  by PKParameter;  
  model lnPKParameter = lnDose / cl alpha=0.1 solution ddfm=kr;  
run;
```

For FE-HS, the following endpoints will be analyzed as described in section 3.3:

- Food Effect analysis:

- o  $C_{\max}$
- o  $AUC_{0-t}$
- o  $AUC_{0-\infty}$
- o  $T_{\max}$

[REDACTED]

- [REDACTED]
- [REDACTED]
- [REDACTED]
- [REDACTED]
- [REDACTED]
- [REDACTED]
- [REDACTED]
- [REDACTED]

[REDACTED]

- [REDACTED]
- [REDACTED]
- [REDACTED]

**11.1** [REDACTED]

[REDACTED]

**11.2** [REDACTED]

[REDACTED]

**11.3** [REDACTED]

[REDACTED]

- [REDACTED]
- [REDACTED]
- [REDACTED]
- [REDACTED]
- [REDACTED]
- [REDACTED]
- [REDACTED]
- [REDACTED]
- [REDACTED]

[REDACTED]

[REDACTED]

[REDACTED]

[REDACTED]

[REDACTED]

[REDACTED]

[REDACTED]

[REDACTED]

[REDACTED]

[REDACTED]

[REDACTED]

[REDACTED]

[REDACTED]

[REDACTED]

[REDACTED]

[REDACTED]

[REDACTED]

[REDACTED]

[REDACTED]

[REDACTED]

[REDACTED]

**11.7** [REDACTED]

[REDACTED]

[REDACTED]

[REDACTED]

[REDACTED]

[REDACTED]

[REDACTED]

[REDACTED]

[REDACTED]

